- For the purpose of internal planning and for reporting to regulatory authorities, the primary analysis results of the urothelial carcinoma secondary cohort will be updated based on a data cut-off date on Oct 7, 2015, as well as on the cut-off dates for the urothelial carcinoma efficacy expansion cohort, i.e. i) 4 months after start of treatment of the 109th subject (Jan 18, 2016); ii) 6 months after start of treatment of the 109th subject (Mar 19, 2016), and iii) 6 months after start of treatment of the last subject enrolled in the efficacy expansion cohort. The efficacy endpoints such as BOR, PFS, OS, and safety endpoints such as the occurrence of TEAE will be included for these additional analyses.
- The interim analysis 13 weeks after the start of treatment of the 30th subject in the urothelial carcinoma efficacy cohort was not performed. Interim analyses will be conducted at 4 and 6 months after the last subject's first dose of study treatment for the 109 subjects enrolled in the urothelial carcinoma efficacy expansion cohort prior to Protocol Amendment 13. The results of these analyses may be subject to reporting to regulatory authorities. The interim analysis is considered positive if the lower limit of the 95% CI of the confirmed BOR exceeds 10%. The following subsets of the cohort are used for the interim analysis when 109th subject has been followed up for 4 months:
 - All subjects first dosed prior to or up to the cut-off date (analysis of safety)
 - All dosed subjects with at least 4 months follow-up as of the cut-off date (analysis of BOR, PFS, OS)
- The following subsets of the cohort will be used for the interim analysis when 109th subject has been followed up for 6 months:
 - All subjects first dosed prior to or up to the cut-off date (analysis of safety)
 - All dosed subjects with at least 13 weeks follow-up as of the cut-off date (BOR, PFS, OS, DR, TTR)
 - All dosed subjects with at least 6 months follow-up as of the cut-off date (BOR, PFS, OS, DR, TTR)
- Analyses on the corresponding PD-L1 positive subsets will be performed depending on PD-L1 data availability at the time of the analysis.
- CTCAE version 4.03 was utilized for laboratory toxicity grading in place of version 4.0 for outputs relating to the Interim Escalation and Expansion CSR.
- Addition of TTR according to modified irRC and to RECIST 1.1 criteria, respectively, per investigator assessment.

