- For the efficacy expansion cohorts and the urothelial carcinoma secondary cohort:
 - TTR according to RECIST 1.1, per IERC

10 Analysis Sets

The following analysis sets are defined for the dose expansion phase and summarized in Table 4:

- Screening analysis set (SCRN): all subjects who signed informed consent form (ICF).
- PK analysis set (PKAS): a subset of the safety analysis set and will include patients who have at least one post-dose concentration measurement above the lower limit of quantitation (LLOQ) for avelumab.
- Safety analysis set (SAF): all subjects who have received at least 1 dose of study treatment.
- Full analysis set (FAS): all subjects who have received at least 1 dose of study treatment.
 - PD-L1 positive (5% cut-off) FAS (urothelial carcinoma efficacy expansion cohort): all PD-L1+ subjects (defined as those with at least 5% of the tumor cells showing PD-L1 membrane staining $\geq 1+$ assessed by immunohistochemistry) who have received at least 1 dose of study treatment.
 - PD-L1 positive (1% cut-off) FAS (NSCLC cohorts): all PD-L1+ subjects (defined as those with at least 1% of the tumor cells showing PD-L1 membrane staining $\geq 1+$ assessed by immunohistochemistry) who have received at least 1 dose of study treatment.
- Efficacy analysis set (EFF, efficacy expansion cohorts): all subjects who have received at least 1 dose of study treatment and have measurable disease at baseline according to IERC assessment.
 - PD-L1 positive EFF (urothelial carcinoma efficacy expansion cohort): all PD-L1+ subjects (defined as those with at least 5% of the tumor cells showing PD-L1 staining $\geq 1+$ assessed by immunohistochemistry) who have received at least 1 dose of study treatment and have measurable disease at baseline according to IERC assessment.
- Efficacy analysis set (primary and secondary expansion cohorts): all subjects who have received at least 1 dose of study treatment and have measurable disease at baseline according to investigator assessment.

The definition of the SAF and the FAS are identical in this non-randomized study; the SAF will be used for the safety analysis and the FAS will be used for efficacy analysis. The PD-L1 positive FAS will be the primary analysis population for the primary endpoint of BOR by IERC in the urothelial carcinoma efficacy expansion cohort, whereas for the other efficacy expansion cohorts the primary analysis population will be the FAS.

Table 4 Summary of Analysis Sets and Associated Analyses

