Analysis Set	Data/Endpoints	Cohorts
SAF	Disposition, baseline, safety, PD-L1 and biomarker, CD8, exposure, immunogenicity	All expansion cohorts
PKAS	PK data	All expansion cohorts
FAS	Efficacy (BOR, PFS, TTR, OS, subgroup analysis, lesion assessment)	All expansion cohorts
PD-L1 positive (5% cut-off) FAS	Efficacy (BOR, PFS, TTR, DR, OS, subgroup analysis, lesion assessment)	Urothelial carcinoma efficacy cohort
PD-L1 positive (1% cut-off) FAS	Efficacy (BOR, PFS, TTR, DR, OS, subgroup analysis, lesion assessment)	NSCLC cohorts
EFF	Efficacy (sensitivity analysis)	All expansion cohorts
PD-L1 positive EFF	Efficacy (sensitivity analysis)	Urothelial carcinoma efficacy cohort
EFF	BOR at 13 weeks (75 subjects interim analysis)	Primary cohorts

For interim analysis, all dosed subjects up to and including the data cut-off date will be included for the analysis. Additionally, two subsets of the population will be defined for interim analysis, dosed subjects with ≥ 6 or ≥ 13 weeks follow-up period up to the data cut-off date. The follow-up period is calculated from the first dose date to the data cut-off date. The analysis of BOR or associated subgroup analysis by PD-L1 status will be based on the two subset populations. The subset populations may also be used for the summary of demographic or other baseline data.

11 General Specifications for Statistical Analyses

- Statistical analyses will be performed using electronic case report form (eCRF) data obtained until a clinical cut-off date.
 - The primary data cut-off for expansion cohorts is 6 months after the last subject started the treatment.
 - The interim data cut-off is 13 weeks after the pre-specified number of subjects started the treatment. For example, an interim analysis will be conducted after the first 75 subjects in each primary cohort have reached the time point of the second post-baseline tumor assessment scheduled in Week 13, i.e. 13 weeks after start of treatment of the 75th subject. There may be minor deviation from this requirement due to combined data transfer used for multiple interim analyses, i.e. a few subjects may not reach the time point for the second post-baseline tumor assessment scheduled in Week 13, which is considered as acceptable.
 - Final data cut-off will be 1 year after the last subject in the expansion phase receives his or her last dose of avelumab.

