16.4.4 Relation of Pharmacokinetics to Efficacy in Urothelial Carcinoma Cohorts

The exposure-response analysis will include subjects with urothelial carcinoma from the Full Analysis Set (secondary cohort of urothelial carcinoma and efficacy expansion cohort of urothelial carcinoma). The analyses will be based on a data cut-off for the urothelial carcinoma efficacy expansion cohort, i.e. 6 months after start of treatment of the 109th subject.

The objectives of this exploratory population exposure response analysis are: To assess the relationships between objective response (OR), overall survival (OS), and progression-free survival (PFS) with avelumab exposure (e.g., single dose trough concentration ($C_{\text{trough_sd}}$), steady-state $C_{\text{trough_ss}}$), and steady-state AUC_{ss}, and single dose AUC_{sd}) in the presence of other relevant covariates.

For OR, the patients will be classified as responder or non-responder based on best overall response (BOR) according to RECIST 1.1 following IERC assessment (responder: CR and PR; non-responder: stable disease [SD], progressive disease [PD], non-evaluable [NE]). OS and PFS will be reported in months.

Population PK parameters, as determined by the final population modeling analysis will be used to derive individual exposure metrics including, but are not limited to $C_{\text{trough_sd}}$, $C_{\text{trough_ss}}$, AUC_{ss} and AUC_{sd}. In addition, observed concentration values (i.e. observed single dose C_{trough} , observed steady-state C_{trough}) may be used to represent exposures.

Multivariable regression models will be employed with a stepwise variable selection process. The covariates will be inserted subsequently to the regression model starting with the covariate linked to the smallest p value (corresponding to the Wald chi-square statistic, given the covariates degrees-of-freedom) not yet included to the model if the corresponding p value is below or equal the inclusion threshold of 15%. After each forward step (i.e. inclusion of a new covariate) the new larger regression model passes a backward step, in which subsequently all covariates are excluded (starting with the covariate linked to the highest p value) if their Wald chi-square p-values lie above the exclusion threshold of 40%. The stepwise procedure stops when no further effect can be added or the previously added effect in the forward step was removed in the next backward step.

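### The urothelial exposure-response models of objective response set no minimum follow-up, so subjects dosed too recently to have responded enter as non-responders

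*SAP*

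**What the plan says.** Expansion SAP, Section 16.4.4 defines its own population: "The exposure-response analysis will include subjects with urothelial carcinoma from the Full Analysis Set", covering both the secondary and the efficacy urothelial cohorts. Section 10 defines that set: "Full analysis set (FAS): all subjects who have received at least 1 dose of study treatment". The data cut-off is "6 months after start of treatment of the 109th subject", which Section 9 dates: "6 months after start of treatment of the 109th subject (Mar 19, 2016". For objective response, subjects are split by best overall response (BOR) under RECIST 1.1 as assessed by the independent endpoint review committee (IERC), with the failure group given as "non-responder: stable disease [SD], progressive disease [PD], non-evaluable [NE". Section 16.4.4 does not limit the efficacy cohort to its first 109 subjects, sets no minimum follow-up, and does not say whether the response must be confirmed.

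Other parts of the same SAP do restrict follow-up for BOR:

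- Section 9, at this same cut-off, keeps all subjects dosed by the cut-off for safety only. For efficacy it lists "All dosed subjects with at least 13 weeks follow-up as of the cut-off date (BOR, PFS, OS, DR, TTR" and, separately, those with at least 6 months.
- Section 10, for interim analyses, defines subsets with at least 6 and at least 13 weeks and states: "The analysis of BOR or associated subgroup analysis by PD-L1 status will be based on the two subset populations".
- Section 16.2 allows the two urothelial cohorts to be pooled for efficacy from subjects with at least 6 months of follow-up.

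**The concern.** Under Sections 6 and 8.1 the efficacy cohort is planned at 200, and the 109 are only those enrolled before Protocol Amendment 13. Anyone first dosed between the 109th subject and 19 March 2016 has under 6 months of follow-up, but belongs to the full analysis set and so to the exposure-response data.

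A subject not yet scanned has a BOR of NE; Section 16.2 lists the absence of post-baseline assessments as a reason for NE. A single partial response with nothing evaluable after it becomes SD or NE under Table 6 of Section 16.1. Section 16.4.4 codes both as failures. The PFS and OS models censor such subjects. The logistic and Emax models of response (Sections 16.4.4.1 and 16.4.4.2) cannot, so calendar time since first dose is recorded as treatment failure. At stake is the fitted probability of response at each exposure.

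**Working it through.** **Cut-off dates.** Section 9 gives two cut-offs for the 109th subject: "4 months after start of treatment of the 109th subject (Jan 18, 2016" and "6 months after start of treatment of the 109th subject (Mar 19, 2016". A first dose on about 19 September 2015 gives 121 days to the first and 182 days to the second, so the two dates agree with each other and with the stated 4 and 6 months.

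**Earliest possible response.** Protocol 7.1.2.2 puts the first scan at Week 7 (Day 43) with a 5-day early window, then every 6 weeks. SAP 16.1 requires confirmation no sooner than 4 weeks later.

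- Any response: Day 43 − 5 = Day 38, or 37 days after first dose.
- Confirmed response at the earliest: Day 38 + 28 = Day 66, or 65 days.
- Confirmed response on schedule: Week 13 (Day 85), or 84 days. The SAP's own filter is 13 weeks, or 91 days.

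**How many subjects are too recent.** The mature set is 44 (secondary cohort) + 109 = 153. Let k be the number first dosed after the 109th and by the cut-off. The documents do not give k; the planned size allows 0 to 200 − 109 = 91. As an assumption, let accrual be uniform from the date of Amendment 13 (20 October 2015, Protocol Appendix IV), which is 151 days before the cut-off. The expected number with under d days is k × d/151, out of 153 + k:

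- under 91 days: 91/151 = 60% of later subjects
- under 65 days: 65/151 = 43%
- under 37 days: 37/151 = 24.5%

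If the mature response rate is r and a share f of the data is forced to zero, the observed rate is r(1 − f). For illustration r = 7/44 = 15.9%, the secondary-cohort figure in Protocol 3.5.5.3. Each cell gives f, then the rate as it would read.

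| k | N = 153 + k | Under 13 weeks | Before Day 66 | Before Day 38 |
|---|---|---|---|---|
| 0 | 153 | 0%; 15.9% | 0%; 15.9% | 0%; 15.9% |
| 20 | 173 | 7.0%; 14.8% | 5.0%; 15.1% | 2.8%; 15.4% |
| 50 | 203 | 14.8%; 13.5% | 10.6%; 14.2% | 6.0%; 14.9% |
| 91 | 244 | 22.5%; 12.3% | 16.1%; 13.3% | 9.1%; 14.4% |

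The 13-week column treats everyone below the SAP's filter as a non-responder. The Day 66 column is the certain minimum if response must be confirmed, and the Day 38 column is the certain minimum if it need not be. If accrual is instead uniform from 19 September 2015 (182 days), the 13-week shares are 5.8%, 12.3% and 18.6%, and the rate reads 15.0%, 13.9% and 12.9%.

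**Intercept and slope.** At k = 91 the logit of the response rate moves from ln(0.159/0.841) = −1.67 to ln(0.123/0.877) = −1.96, a downward shift of about 0.30. A logistic simulation used an assumed true slope of 0.70 per SD of exposure, 60% of later subjects too recent, and 600 replicates per setting. With recency unrelated to exposure, the mean slope without and with the filter was 0.71 and 0.72 at k = 20, 0.69 and 0.72 at k = 50, and 0.67 and 0.71 at k = 91. If recent subjects' exposure metric is assumed to differ by 0.5 SD, the unfiltered slope at k = 91 is 0.50 (higher exposure) or 0.79 (lower exposure).

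**The case against.** The strongest reply is that Section 16.4.4 should be read with the rest of the SAP. It uses a cut-off for which Section 9 already sets follow-up subsets for BOR, and it analyses the same two cohorts that Section 16.2 pools with at least 6 months. On that view only a cross-reference is missing. But 16.4.4 cites none of those rules and names the plain full analysis set, and Section 12.1 counts the full analysis set with a follow-up period as a separate line from the plain one. Section 10 would not settle it either: its 6-week subset is too short for a confirmed response.

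Several limits do stand. The analysis is labelled exploratory, k is unknown and could be 0, and 16.4.4 does not say that BOR is confirmed. If unconfirmed BOR is meant, only subjects not yet scanned are certain failures.

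A reader might also infer more than the documents support:

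- *That every subject dosed after the 109th is a forced failure*, which would be 20/173 = 12%, 50/203 = 25% or 91/244 = 37% of the data. Those with 13 to 26 weeks have passed both the Week 7 and Week 13 scans. These figures are ceilings, reached only if all later subjects started after 19 December 2015. Section 9 lists a 13-week subset apart from the 6-month one, which implies that subjects between the two were expected.
- *That sparse sampling pulls recent subjects' exposure towards the mean.* Protocol 7.5.2 schedules eight samples by Day 43 (four pre-dose, four post-dose), and SAP 16.4.3 fits the population model jointly with other studies. Material shrinkage is not shown.
- *That regimen decisions rest on this curve.* Protocol 3.5.1 argues mainly from NSCLC and mentions urothelial response only as a non-significant trend.

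**Conclusion.** The point holds for the objective-response models. As written, Section 16.4.4 counts subjects who have not had time to respond as non-responders, and it departs without explanation from the filters the SAP sets for BOR in the same cohorts. The main effect is downward bias in the response level. With 20, 50 or 91 later subjects and uniform accrual from 20 October 2015, about 7%, 15% or 22% of the data would have under 13 weeks, and 15.9% would read as 14.8%, 13.5% or 12.3%. A later start of accrual would raise these shares; no later subjects would mean no bias.

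A reader might infer that the exposure slope is substantially diluted. The documents do not support that: attenuation is slight unless time since first dose is related to the exposure metric, and they give no evidence that it is. The PFS and OS models are not affected in this way, because recent subjects are censored. Because the analysis is exploratory, the consequence is limited, but the bias is avoidable.

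**What to change.** In Section 16.4.4, state that the logistic and Emax models of objective response use urothelial subjects with at least 6 months from first dose to the cut-off (the 44 secondary plus the first 109 efficacy subjects), with at least 13 weeks as a sensitivity set, in line with Sections 9 and 16.2. State that response means confirmed BOR by IERC. The PFS and OS models may keep all dosed subjects because censoring applies, but Section 9 assigns PFS and OS at this cut-off to the same follow-up subsets as BOR, so the difference should be stated. Report the number first dosed between the 109th subject and 19 March 2016.

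The cost is a few sentences in the SAP and one filter in the program. The downside is that later-enrolled subjects leave the response models until their data mature.

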The interpretation and final inclusion of the covariate(s) in the final model will depend on biological plausibility, dataset attributes and clinical significance of the covariate in question.

Covariates to be tested consider potential prognostic factors including the following in Table 8:

Table 8 Table of potential covariates for regression models

Category	Covariates
Demographics	race, sex, age, baseline body weight
Prior Treatments	Prior radiotherapy (Y/N), Number of prior anti-cancer drug therapies, Prior adjuvant therapy
Safety laboratory information at baseline	Albumin, alkaline phosphatase, bilirubin, alanine aminotransferase, aspartate aminotransferase, platelet count, lactate dehydrogenase at baseline, eGFR*, hemoglobin
Disease-related laboratory values	PD-L1 status
Disease Status/Treatment	Baseline ECOG Status (0/1/2) Concomitant medication of Corticosteroids for systemic use (Y/N) Metastatic disease** at enrolment (study entry) – liver metastasis, other metastasis, no metastasis Number of non-target lesions at baseline Tumor burden at baseline (mm) Tumor sub-site (Lower tract / Upper tract) Eligibility of platinum-based therapy *** (Y/N)

*eGFR is calculated as follows:

$$eGFR=32788*CREAT^{**}(-1.154)*AGE^{**}(-0.203) + SEX*0.742+MRACE*1.210$$

where CREAT is serum creatinine (µmol/L), AGE is age (years), Sex is a flag for sex (0 for males, 1 for females) and MRACE is a flag for race (1 for Black or African American, 0 otherwise). $CREAT(mg/dL)*88.4=CREAT(\mu mol/L)$

** as evaluated by local or central tumor assessments

*** Subjects are considered eligible for platinum-based therapy in case they receive cisplatin as a prior anti-cancer treatment.

Missing time-invariant categorical covariates will be set to be a separate category distinct from other categories. If the percentage of missing values is below 10%, the missing values should be imputed based on modeler’s decision to balance the distribution of the categorical covariate. Missing time-invariant continuous covariates will be to the population median or excluded from the analysis if the percentage of missing values is equal or larger than 25%.

The exposure-response relationship for BOR will be performed using R or NONMEM 7.3. Exposure-response calculations regarding PFS and OS will be performed using the software SAS 9.3 or R.

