$$eCcr = \frac{(140 - \text{Age}) \times \text{Weight(kg)} \times \text{Constant}}{\text{Serum Creatinine } (\mu\text{mol/L})}$$

where the constant is 1.23 for men and 1.04 for women.

The corrected eCcr is derived as:

$$\text{Corrected eCcr (ml/min/1.73m}^2) = eCcr \times 1.73 / \text{BSA}$$

where BSA (body surface area, m²) = ([baseline height (cm) × weight (kg)] / 3600)^{0.5}.

The following are non-CTCAE gradable parameters collected in this study, their abnormalities are assessed as low, high, normal based on the comparison of observed values with normal ranges.

- Hematology: hematocrit, red blood cell (RBC), reticulocytes, mean corpuscular hemoglobin (MCH), mean corpuscular volume (MCV), mean corpuscular hemoglobin concentration (MCHC).
- Serum Chemistry: chlorine, C-reactive protein, lactate dehydrogenase (LDH), total protein, total urea, uric acid.
- Hormone: adrenocorticotrophic hormone (ACTH), anti-nuclear antibody (ANA), anti-neutrophil cytoplasmic antibody (ANCA), rheumatoid factor (RF), free thyroxine (Free T4), thyroid-stimulating hormone (TSH).

Laboratory abnormalities will be summarized using the worst grade during the on-treatment period. For these parameters which are graded with two toxicities such as potassium (hypokalemia/hyperkalemia), the toxicities will be summarized separately. Low direction toxicity (eg. hypokalemia) grades at baseline and post-baseline will be set to 0 when the variables are derived for summarizing high direction toxicity (e.g. hyperkalemia), and vice versa.

The change and percent change from baseline will be derived for parameters with numeric results.

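### The SAP's eGFR formula adds the sex and race factors (0.742 and 1.210) as 0/1 terms instead of multiplying by them, so the covariate is wrong for every woman and every Black subject

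*SAP*

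**What the plan says.** Expansion SAP, Section 16.4.4, plans logistic regression for objective response and Cox models for PFS and OS, relating avelumab exposure to outcome in the urothelial carcinoma cohorts. Covariates are chosen stepwise: "Covariates to be tested consider potential prognostic factors including the following in Table 8". eGFR is listed there among the baseline safety laboratory values.

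The Table 8 footnote gives its formula: 32788 × CREAT^(−1.154) × AGE^(−0.203), followed by a plus sign and then "SEX*0.742+MRACE*1.210". The coding is explicit: SEX equals 1 in women and 0 in men, and MRACE equals 1 in Black or African American subjects and 0 in everyone else. Creatinine is in µmol/L, with a conversion from mg/dL supplied ("CREAT(mg/dL)*88.4=CREAT"). The footnote neither names nor cites a source equation, and no other section gives a different version.

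The SAP has one other renal formula, the Cockcroft-Gault creatinine clearance in Section 17.3. There sex enters as a multiplier: "where the constant is 1.23 for men and 1.04 for women".

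**The concern.** A coefficient of 0.742 or 1.210 attached to a 0/1 flag moves eGFR by about one unit. Nobody specifies a sex or race adjustment to three decimals in order to shift a value near 80 by about 1%. The numbers have the size of ratios and look like multipliers that have been turned into added terms. The sign for sex is also wrong by the SAP's own standard: the printed formula raises the value for women, while Section 17.3 lowers it.

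If the covariate is programmed as printed, renal function is mis-scaled by a different proportion in each sex and race group. Sex and race are themselves Table 8 candidates, so the error is tied to other variables in the same selection. Entry is permissive (p ≤ 0.15 to enter, removal only above 0.40), and variables enter one at a time, so eGFR can be tested or retained without sex or race in the model. Which covariates are kept, and the adjusted exposure effect, could both be affected.

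**Working it through.** The SAP states no eGFR result, so there is no figure to reproduce. The check compares the printed form with the multiplicative form.

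**Inputs.** From the Table 8 footnote: constant 32788, exponents −1.154 and −0.203, factors 0.742 and 1.210, conversion 88.4, SEX = 1 for women, MRACE = 1 for Black or African American subjects. From Section 17.3: sex constants 1.23 and 1.04. Creatinine and age values are assumptions, since the documents give no distribution.

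**Step 1: is the base term sound?** Converting the leading constant to mg/dL gives 32788 / 88.4^1.154 = 186.0, a round constant. The creatinine-age part is coherent, and only the sex and race part is in doubt.

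**Step 2: the two forms.**

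- Printed: base + 0.742 × SEX + 1.210 × MRACE
- Multiplicative: base × 0.742^SEX × 1.210^MRACE

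| Creatinine (µmol/L), age | Base | Non-Black woman: printed / multiplied | Black man: printed / multiplied | Black woman: printed / multiplied |
|---|---|---|---|---|
| 80, 65 | 89.4 | 90.2 / 66.4 (+36%) | 90.6 / 108.2 (−16%) | 91.4 / 80.3 (+14%) |
| 88.4, 68 | 79.0 | 79.7 / 58.6 (+36%) | 80.2 / 95.6 (−16%) | 80.9 / 70.9 (+14%) |
| 110, 70 | 61.0 | 61.8 / 45.3 (+36%) | 62.2 / 73.8 (−16%) | 63.0 / 54.8 (+15%) |

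For the first row, 32788 × 80^(−1.154) × 65^(−0.203) = 89.4; then 89.4 + 0.742 = 90.2 against 89.4 × 0.742 = 66.4.

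Over creatinine 60 to 150 and age 50 to 80, the printed form differs from the multiplicative form by +35.5% to +37.2% (non-Black women), −14.9% to −16.6% (Black men), +13.0% to +16.6% (Black women) and 0% (non-Black men). The percentages hardly depend on the assumed inputs.

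**Step 3: how much does the printed adjustment do?** Over the same grid the base runs from 131.5 to 41.5. A single flag therefore shifts the result by 0.742/131.5 = 0.6% at least and 1.210/41.5 = 2.9% at most.

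**Step 4: can the two forms ever agree?** Set printed equal to multiplied and solve for the base:

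- Non-Black woman: 0.742 / (0.742 − 1) = −2.9, impossible.
- Black man: 1.210 / (1.210 − 1) = 5.8, far below the entry requirement of creatinine clearance above 30 mL/min (Protocol Section 5.3.1; a different renal measure, but the gap is wide).
- Black woman: 1.952 / (0.742 × 1.210 − 1) = 1.952 / (−0.102) = −19.1, impossible.

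So no eligible woman or Black subject receives the multiplicative value.

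**Step 5: direction for sex.** Section 17.3 gives women/men = 1.04/1.23 = 0.85. The printed eGFR gives, for example, 90.2/89.4 = 1.01.

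**Step 6: could the plus signs be misprinted product signs?** No. With 0/1 flags, base × SEX × 0.742 × MRACE × 1.210 is zero for every man and for every subject who is not Black. The flags work as exponents, not as factors.

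**The case against.** The SAP does not cite its eGFR equation, so the multiplicative values are inferred rather than quoted. That is fair. For sex, Section 17.3 supports the direction but not the exact factor (0.85, not 0.742). For race there is no second formula to compare with, and the case rests on the ratio-like size of 1.210. This is a reason to have the source named. It does not make the printed formula plausible.

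The strongest objection concerns impact. The analysis is exploratory and confined to the urothelial cohorts. eGFR is one of more than twenty candidates, and final inclusion also depends on plausibility and clinical judgement. The Emax model for response (Section 16.4.4.2) is written without covariates. Including sex and race as main effects would absorb much of the error. A simulated logistic model gives a sense of scale. It assumed 20% to 35% women, 5% Black subjects, an exposure-eGFR correlation of −0.3 to −0.5, an eGFR log-odds of 0.2 to 0.4 per SD and a true exposure log-odds of 0.4. Using the printed form moved the exposure coefficient about 3% to 14% toward zero with sex and race left out, and by under 2% with both included. The effect is therefore modest, and conditional on what the stepwise procedure keeps, which the plan does not fix in advance. The error also scales with the base value (about 0.258 × base for women), so main effects do not remove it entirely.

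Finally, the operators should be checked against the original PDF because the equation was machine-read. Nothing suggests they were altered, and Step 6 shows that the obvious misreading would not help.

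**Conclusion.** The formula is wrong as written. It gives an incorrect eGFR to every woman and every Black subject: about 36% too high for non-Black women, about 16% too low for Black men and about 14% too high for Black women at typical values. Non-Black men are unaffected. The percentages rest on the multiplicative form being the intended one, which the scale of the constants, the direction in Section 17.3, the failure of the product reading and the intact base constant of 186.0 all support.

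The consequence is limited to the stepwise logistic and Cox exposure-response models in urothelial carcinoma. Distortion of covariate selection or of the exposure effect is a risk, not something demonstrated, and is probably modest. The primary endpoint, alpha and sample size do not depend on it. It should be corrected because an analyst following the SAP would derive a wrong covariate, and Section 5 allows these analyses to go into regulatory submissions and manuscripts.

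**What to change.** Replace the Table 8 footnote formula with

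eGFR = 32788 × CREAT^(−1.154) × AGE^(−0.203) × 0.742^SEX × 1.210^MRACE

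keeping the flag coding and units as they are, and name the source equation so that the constants can be verified. Then compare the programmed derivation with the corrected line. If the program already multiplies, only the text changes. If it follows the printed formula, re-derive the one covariate and repeat the stepwise selection for the response, PFS and OS models.

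Substituting the body-surface-corrected creatinine clearance from Section 17.3 is not needed. It is a different quantity with body weight built in, and body weight is already a Table 8 candidate.

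The cost is a one-line SAP correction, a program check and, at most, one covariate re-derivation with a re-run of exploratory models. No new data are required.
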